### 7.1. Informed consent and patient privacy

The study will be fully discussed with the patient. Any patient wishing to participate must give informed consent prior to any study-related procedures are performed or there is a change in treatment. The patient must also give authorization (US only), data protection consent (Europe only), and other written documentation in accordance with the relevant country and local privacy requirements (where applicable) prior to any study-related procedures are performed or there is a change in treatment.

Each patient who provides informed consent will be assigned a patient number that will be used on patient documentation throughout the study.

### 7.2. Visits and associated procedures

Evaluations should be performed by the same evaluator throughout the study whenever possible.

Unless otherwise specified, procedures are recommended to be done in the order listed.

#### Screening

- Obtain informed consent and authorization
- Review eligibility criteria
- Collect demographic information and medical and ophthalmic history
- Vital signs (blood pressure and pulse rate)
- Urine pregnancy test for women of childbearing potential (confirmed with serum if positive)
- Collect information about concomitant medications and procedures
- Collect blood for central labs
- Perform the following procedures in both eyes:
  - BCVA using ETDRS method following refraction
  - Full ophthalmic examination: slit lamp biomicroscopy, IOP assessment, and dilated indirect ophthalmoscopy examination
  - SD-OCT imaging

- Dilated ultra-wide field (UWF) color fundus photography
- 

**Baseline (Day 0)**

- Review eligibility criteria and reading center confirmation of eligibility
- Query for ocular symptoms
- Vital signs (blood pressure and pulse rate)
- Brief physical exam
- Urine pregnancy test for women of childbearing potential (confirmed with serum if positive)
- Collect information about concomitant medications and procedures
- Perform the following procedures in both eyes:
  - BCVA using ETDRS method following refraction
  - Full ophthalmic examination: slit lamp biomicroscopy, IOP assessment, and dilated indirect ophthalmoscopy examination
  - SD-OCT imaging
  - OCT-A
  - Ultra wide-field fluorescein angiography

After completion of these procedures, and the participant still meets entry criteria, and the central reading center (CRC) has confirmed participant eligibility based on ocular inclusion/exclusion criteria from the screening visit, and the investigator has confirmed patient eligibility based on the results from the blood chemistry, hematology, and urine or serum pregnancy test from the screening visit; the participant will be enrolled

- Perform the following procedures in the study eye:
  - Administer assigned study medication
  - Conduct post-injection assessments at 30 minutes

**Days 28, 56, and 84**

- Query for adverse events and ocular symptoms
- Vital signs (blood pressure and pulse rate)
- Brief physical exam (month 3 only)
- Urine pregnancy test where indicated and positive results confirmed with serum test (low dose group at day 28 prior to second injection; both groups at month 3 only)
- Review concomitant medications and procedures
- Collect blood samples for central lab (month 3 only)
- Perform the following procedures in the study eye (both eyes at month 3)
  - BCVA using ETDRS method following refraction
  - full ophthalmic examination: slit lamp biomicroscopy, IOP assessment, and dilated indirect ophthalmoscopy examination
  - SD-OCT imaging
  - OCT-A
  - Dilated ultra-wide field (UWF) color fundus photography (both eyes at month 3 only)
  - UWF Fluorescein angiogram (month 1 and 3)
  - Administer assigned study medication at day 28 and 56 in low-dose group; day 56 in high dose group
  - Conduct post-injection assessment at 30 minutes

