**Objectives and Endpoints:**

Objective	Endpoint
Primary	
Evaluate the safety and tolerability of AVD-104 in participants with DME	1. Ocular and clinical examinations of participants for any evidence of ocular, systemic adverse or serious adverse events
Secondary	

 
- Evaluate the treatment effect of AVD-104 at multiple doses on central subfield thickness (CST) as measured by Spectral-domain optical coherence tomography (SD-OCT)
 
- Evaluate the treatment effect of AVD-104 at multiple doses on Best-corrected visual acuity (BCVA) using ETDRS ((Early-Treatment Diabetic Retinopathy Study) visual acuity charts
 
	
 
1. Change in CST as measured by SD-OCT at Month 1, 2, and 3
 
2. Change from baseline in BCVA as assessed with the ETDRS visual acuity at Month 1, 2, and 3
 

Exploratory	

 
- [REDACTED]
 
	
 
1. [REDACTED]
 

**Overall Design:** Participants will have evidence of DME secondary to diabetic retinopathy that meets the inclusion criteria.

The primary objective is to evaluate the tolerability and treatment effect of intravitreal injections of AVD-104 in participants with DME. Participants will receive either three injections of low-dose AVD-104 [REDACTED] each 28 days apart or two intravitreal injections of AVD-104 at a dose of [REDACTED] (high-dose) 56 days apart. Serial SD-OCT, UWFA, and OCT-A will be performed to evaluate the treatment effect on central subfield thickness (CST) and areas of non-perfusion. All participants will be followed-up for safety until day 84.

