6. Urine pregnancy tests shall be performed in females of childbearing potential only. The high and low dose groups will be tested at screening, baseline, day 56, and day 84 or termination. The low dose group will be retested again at day 28 before their second injection. If the test is positive at any of these timepoints, then a confirmatory serum pregnancy test must be conducted.
7. Central labs consist of complete blood count and metabolic profile as outlined in [Appendix 2](#).
8. Best-corrected visual acuity measured using Early Treatment of Diabetic Retinopathy Study protocol.

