### **8.5.5. Clinical safety laboratory assessments**

Any significant abnormality noted in systemic values obtained from the clinical laboratory testing (central laboratory) should be reported as possible adverse events. If there is any question that these represent serious abnormalities, both the medical monitor and sponsor should be notified.

- Refer to [Appendix 2](#) for the list of clinical laboratory tests to be performed and to the SoA for the timing and frequency.
- The investigator must review the laboratory report, document this review, and record any clinically relevant changes occurring during the study in the AE section of the CRF. The laboratory reports must be filed with the source documents. Clinically significant abnormal laboratory findings are those which are not associated with the underlying disease, unless judged by the investigator to be more severe than expected for the participant's condition.
- All laboratory tests with values considered clinically significantly abnormal during participation in the study or within [REDACTED] after the last dose of study treatment should be repeated until the values return to normal or baseline. If such values do not return to normal/baseline within a period judged reasonable by the investigator, the etiology should be identified, and the sponsor notified.
- All protocol-required laboratory assessments, as defined in [Appendix 2](#), must be conducted in accordance with the laboratory manual and the SoA.
- If there is an urgent need and laboratory values from a non-protocol specified laboratory assessments performed at the institution's local laboratory require a change in participant management or are considered clinically significant by the investigator (eg, SAE or AE or dose modification), then the results must be recorded in the eCRF.

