## Pregnancy testing

- WOCBP should only be included after a confirmed menstrual period and a negative highly sensitive urine (dipstick or microscopy) pregnancy test
- Pregnancy testing urine testing will be performed at screening, M12, and M24. If the urine test is positive, it should be confirmed by serum testing.
- Pregnancy testing will be performed whenever a menstrual cycle is missed or when pregnancy is otherwise suspected

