#### **Female participants who become pregnant**

- Investigator will collect pregnancy information on any female participant, who becomes pregnant while participating in this study.
- Information will be recorded on the appropriate form and submitted to the sponsor within [REDACTED] of learning of a participant's pregnancy.
- Participant will be followed to determine the outcome of the pregnancy. The investigator will collect follow-up information on participant and neonate, which will be forwarded to the sponsor. Generally, follow-up will not be required for longer than 6 to 8 weeks beyond the estimated delivery date.
- Any termination of pregnancy will be reported, regardless of fetal status (presence or absence of anomalies) or indication for procedure.
- While pregnancy itself is not considered to be an AE or SAE, any pregnancy complication or elective termination of a pregnancy will be reported as an AE or SAE.
- A spontaneous abortion is always considered to be an SAE and will be reported as such.
- Any SAE occurring as a result of a post-study pregnancy, which is considered reasonably related to the study treatment by the investigator, will be reported to the sponsor as described in [Appendix 4](#) While the investigator is not obligated to actively seek this information in former study participants, he or she may learn of an SAE through spontaneous reporting.

Any female participant who becomes pregnant while participating:

- Will discontinue study treatment but not be withdrawn from the study

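### Section 7.2 leaves out the Day 56 pregnancy test that the Schedule of Activities requires before an injection in both groups, and Appendix 5 lists tests that an 84-day trial cannot reach

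*Protocol*

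**What the plan says.** Four places in the protocol bear on pregnancy-test timing after enrolment.

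- **Section 2 (SoA), grid and footnote 6.** The grid marks a test at screening, baseline, Day 28, Day 56 and Day 84. Footnote 6 qualifies the row: "The high and low dose groups will be tested at screening, baseline, day 56, and day 84 or termination". It adds a Day 28 test for the low-dose group, before the second injection.
- **Section 7.2, Days 28, 56 and 84.** A urine test is to be done where indicated, and a parenthesis then says when: "low dose group at day 28 prior to second injection; both groups at month 3 only". The same list gives the dosing: "Administer assigned study medication at day 28 and 56 in low-dose group; day 56 in high dose group".
- **Appendix 5, Pregnancy testing.** "Pregnancy testing urine testing will be performed at screening, M12, and M24". The appendix also asks for a negative test before inclusion, and adds event-driven testing: "Pregnancy testing will be performed whenever a menstrual cycle is missed or when pregnancy is otherwise suspected".
- **Appendix 5, Female participants who become pregnant.** Such a participant "Will discontinue study treatment but not be withdrawn from the study".

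The length of the trial is set in the Synopsis: "All participants will be followed-up for safety until day 84".

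**The concern.** Footnote 6 reflects a clear decision to test before each injection. Section 7.2, the ordered procedure list for each visit, does not carry that decision through: its last word, "only" in "low dose group at day 28 prior to second injection; both groups at month 3 only", rules out Day 56, when both groups receive their final injection. Appendix 5 offers a third schedule whose later time points match no visit in this trial.

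The rule that pregnancy ends study treatment protects a participant only if the pregnancy is found before she is dosed. A site that follows Section 7.2 as written would deviate from footnote 6 and could inject a woman whose pregnancy nobody yet suspects. The matter is participant safety and protocol conduct. The descriptive analyses in the SAP are not touched.

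**Working it through.** The plan states no figure to reproduce. The check sets the schedules side by side and counts days.

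**Inputs**
- Injection days: low dose Days 0, 28 and 56; high dose Days 0 and 56 (SoA; Section 7.2).
- Visit window: ±7 days at Days 28, 56 and 84 (SoA). Baseline is Day 0.
- Test days: SoA footnote 6; Section 7.2 (screening, baseline, and the later visits); Appendix 5.

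**Scheduled test at each injection visit**

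| Group | Injection | Footnote 6 | Section 7.2 |
|---|---|---|---|
| Low dose | Day 0 | yes | yes |
| Low dose | Day 28 | yes | yes |
| Low dose | Day 56 | yes | **no** |
| High dose | Day 0 | yes | yes |
| High dose | Day 56 | yes | **no** |

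Injection visits: 3 + 2 = 5. Footnote 6 covers 5 of 5. Section 7.2 covers 2 + 1 = 3 of 5, and both omissions are Day 56.

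**Days from the last scheduled test to the Day 56 injection under Section 7.2**
- High dose: the last test is at baseline. 56 − 0 = 56 days; with the window, 49 − 0 = 49 to 63 − 0 = 63.
- Low dose: the last test is at Day 28. 56 − 28 = 28 days; shortest 49 − 35 = 14, longest 63 − 21 = 42.
- Under footnote 6 the gap is 0 days in both groups.

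**Appendix 5.** M12 and M24 are not in the abbreviation list. The calculation assumes that M means month, and takes 28 days per month because the protocol calls Day 84 month 3 (84 / 3 = 28).
- M12: 12 × 28 = Day 336, which is 336 − 84 = 252 days after the last visit.
- M24: 24 × 28 = Day 672, which is 672 − 84 = 588 days after the last visit.

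Of the three Appendix 5 time points, only screening exists in this trial. The exact day counts depend on the assumption. That no visit carries either label does not.

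**The case against.** The strongest reply is that the test is already scheduled. The SoA grid and footnote 6 agree on Day 56, and the protocol sends the reader to the SoA for timing in several places. Section 8.5.5 refers to Appendix 2 "for the list of clinical laboratory tests to be performed and to the SoA for the timing and frequency", and also makes it mandatory to perform the Appendix 2 assessments according to the SoA. If Table 3 in Appendix 2 lists the pregnancy test, the SoA would already govern it. The contents of that table are not visible in the public copy, so this can be neither confirmed nor excluded. Even if it is so, Section 7.2 would still contradict the SoA and would still need correcting.

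The harm is also contingent. It needs a site that works from Section 7.2 rather than the grid, and a woman who conceives despite the contraception requirement and a negative baseline test and who does not suspect pregnancy. Event-driven testing after a missed cycle would catch some cases, especially over a 56-day gap. All of this reduces the likely number affected, in a trial of at most 30 participants. But event-driven testing depends on recognition and reporting, and footnote 6 shows that the sponsor wanted a scheduled check as well.

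It is fair to say that M12 and M24 do little damage by themselves. No site can act on them, and Appendix 5 does not forbid other tests. They look like text carried over from another protocol. The 3-of-5 count likewise adds little to the plain statement that Day 56 is missed in both groups.

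These points bear on weight. None of them removes the conflict.

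**Conclusion.** The concern holds. Section 7.2 contradicts SoA footnote 6 at the Day 56 injection visit in both groups, and Appendix 5 lists two time points outside the trial. Followed as written, Section 7.2 gives the final injection with no scheduled pregnancy test for 56 days in the high-dose group (49 to 63) and 28 days in the low-dose group (14 to 42). The high-dose group is the more exposed: its second injection would follow no scheduled test since baseline.

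This is an internal inconsistency in a safety procedure that should be fixed. It has no bearing on sample size, endpoints or analyses. The number of women of childbearing potential is not given, so the number affected is unknown and may be zero. The Day 56 finding rests on the visible text and needs no assumption. The day counts for M12 and M24 assume that M means a 28-day month.

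**What to change.** 1. In Section 7.2, under Days 28, 56 and 84, add a urine pregnancy test before the Day 56 injection in both groups, and remove the restriction to month 3.
2. In Appendix 5, replace the screening, M12 and M24 timings with the footnote 6 schedule: screening, baseline, Day 28 (low dose), Day 56, and Day 84 or termination. Keep the pre-inclusion test and the testing prompted by a missed cycle or suspected pregnancy.
3. State once that the SoA with footnote 6 governs the timing of pregnancy tests.

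The cost is a change of protocol wording. It adds no visit, and no test beyond those footnote 6 already schedules.

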## 8. ADVERSE EVENTS

The definitions of an AE and SAE can be found in [Appendix 4](#).

AE will be reported by the participant (or, when appropriate, by a caregiver, surrogate, or the participant's legally authorized representative).

The investigator and any designees are responsible for detecting, documenting, and reporting events that meet the definition of an AE or SAE and remain responsible for following up AEs that are serious, considered related to the study treatment or other aspects of the study, or that caused the participant to discontinue the study treatment or other aspects of the study (see [Section 9](#)).

### 8.1. Time period and frequency for collecting AE and SAE information

All AEs and SAEs will be collected from the start of treatment until the final follow-up visit at the time points specified in the SoA ([Section 2](#)).

Medical occurrences that begin before the start of study treatment but after obtaining informed consent will be recorded on the Medical History/Current Medical Conditions section of the case report form (CRF).

All SAEs will be recorded and reported to the sponsor or designee within [REDACTED] as indicated in [Appendix 4](#). The investigator will submit any updated SAE data to the sponsor within [REDACTED] of it being available.

Investigators are not obligated to actively seek AE or SAE in former study participants. However, if the investigator learns of any SAE, including a death, at any time after a participant has been discharged from the study, and he/she considers the event to be reasonably related to the study treatment or study participation, the investigator must promptly notify the sponsor.

The method of recording, evaluating, and assessing causality of AE and SAE and the procedures for completing and transmitting SAE reports are provided in [Appendix 4](#)

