## 2. SCHEDULE OF ACTIVITIES (SOA)

Activity	Screen	Baseline					
		Predose	Dose	Post Dose	Day 28	Day 56	Day 84
Day/month	Day -28 to -1	Day 0			±7	±7	±7
Window (±days)							
Informed Consent/HIPAA	X						
Eligibility Criteria	X	X					
Medical History	X						
Ocular History 	X						
Demographics 	X						
Review adverse events/ocular symptoms 		X		X	X	X	X
Record TEAEs				X	X	X	X
Vital signs 	X	X			X	X	X
Brief Physical examination 		X					X
Urine/Serum Pregnancy Test 	X	X			X	X	X
Prior/Con Medications	X	X			X	X	X
Central Labs 	X						X
BCVA by ETDRS 	OU	OU			SE	SE	OU
Slit Lamp Biomicroscopy	OU	OU			SE	SE	OU
IOP	OU	OU		SE	SE	SE	OU
Indirect Ophthalmoscopy	OU	OU			SE	SE	OU
SD-OCT	OU	OU			SE	SE	OU
OCT-A		OU			SE	SE	OU
Color fundus photographs	OU						OU
Fluorescein angiogram		OU			SE		OU
Select/Confirm Study Eye		X					
IVT injection high-dose group (n=15)			SE			SE	

CONFIDENTIAL

Activity	Screen	Baseline			Post Dose	Day 28	Day 56	Day 84
		Predose	Dose					
Day/month	Day -28 to -1	Day 0						
Window (±days)					±7	±7	±7	
IVT injection low-dose group (n=15)			SE		SE	SE		

Abbreviations AST = BCVA = best-corrected visual acuity; Con = concomitant; ETDRS = early-treatment diabetic retinopathy study; HIPPA = Health Insurance Portability and Accountability Act; IOP = intraocular pressure; IVT = intravitreal injection; OCT-A = Optical coherence tomographic angiography ; SD-OCT = spectral-domain optical coherence tomography; TEAE = treatment emergent adverse event; OU = Both eyes; SE = Study eye

1. Ocular history shall include but is not limited to diabetic retinopathy-related events (hemorrhage, previous laser, etc.), eye involvement, and localization (central versus non-central).
2. Demographics include age, gender, race, ethnicity, height, and weight.
3. The severity of ocular symptoms (burning/stinging, itching, foreign body, discomfort, dryness, photophobia, and pain) shall be evaluated on a visual analogue scale of 0 to10.
4. Vital signs include temperature (oral, tympanic, or temporal), resting heart rate, and blood pressure.
5. Brief physical examination includes appearance, mood, and affect only. Physical examination for symptom driven findings may be conducted at any time during the study.

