5.1 Adverse Events

The definitions of an Adverse Event (AE) and Serious Adverse Event (SAE) – as well as the method of recording, evaluating, and assessing causality of AE and SAE and the procedures for completing and transmitting SAE reports - can be found in Appendix 4 of the Study Protocol.

All AEs and SAEs will be collected from the start of treatment until the final follow-up visit at the time points specified in the SoA (Section 2 of Study Protocol).

Medical occurrences that begin before the start of study treatment but after obtaining informed consent will be recorded on the Medical History/Current Medical Conditions section of the case report form (CRF) and will be tabulated accordingly.

Details of all pregnancies in female participants and, if indicated, female partners of male participants will be collected after the start of study treatment and until 35 days after the last dose. Abnormal pregnancy

outcomes (e.g., spontaneous abortion, fetal death, stillbirth, congenital anomalies, ectopic pregnancy) are considered SAEs and will be tabulated accordingly.

7

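### AE and SAE collection starts at the first injection, so harm from study procedures done before it, including the Day 0 angiogram, is recorded as medical history

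*Protocol*

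**What the plan says.** Protocol 8.1 opens the AE and SAE window at the start of treatment and closes it at the final follow-up visit. It then deals with the interval before that: "Medical occurrences that begin before the start of study treatment but after obtaining informed consent will be recorded on the Medical History/Current Medical Conditions".

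SAP 5.1 carries both sentences into the analysis. The window is "All AEs and SAEs will be collected from the start of treatment until the final follow-up visit", and earlier occurrences go to the "Medical History/Current Medical Conditions section of the case report form (CRF) and will be tabulated accordingly".

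Study procedures begin before that window. Screening (Day -28 to -1) includes a blood draw and a dilated examination. The Day 0 list in Protocol 7.2 includes "Ultra wide-field fluorescein angiography", and the Schedule of Activities puts it in the Predose column. Enrolment and the first injection come later, introduced by "After completion of these procedures, and the participant still meets entry criteria". Angiography is repeated at Day 28 and Day 84.

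The Schedule of Activities has a row "Review adverse events/ocular symptoms" that is marked at Day 0 Predose. The row for recording treatment-emergent events is first marked after the dose, and the Day 0 visit text asks about ocular symptoms only.

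**The concern.** The rule sorts events by date alone. Pre-dose events that reflect the participant's background health belong in medical history. Events caused by something the protocol required are a different matter: they are a risk of taking part, and safety and tolerability is the primary objective.

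Two consequences follow. First, the same reaction to the same procedure is classified differently according to which angiogram produced it. Second, an event serious enough to keep someone from being dosed is the one least likely to appear in the safety tables, because SAP 3.1 defines the Safety population by receipt of at least one dose and runs every table on it.

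**Working it through.** The plan states no figure on this point, so the main check is to set the passages in time order.

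1. **Consent and screening, Day -28 to -1.** Blood draw, dilated examination and imaging. The 8.1 window is not open.
2. **Day 0, before the dose.** Protocol 7.2 says that "procedures are recommended to be done in the order listed". On that list the symptom query comes early, angiography comes last among the two-eye procedures, and the injection follows. Protocol 4.1.1 also places the baseline angiogram before randomisation. The window is still closed, and the only listed query precedes the angiogram.
3. **First injection.** The window opens.
4. **Days 28, 56 and 84.** The visit text asks about adverse events as well as symptoms. Angiography at Days 28 and 84 falls inside the window.

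Next, where a reaction to the Day 0 angiogram would appear:

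| | Participant later dosed | Participant not dosed |
|---|---|---|
| AE and SAE tables | no, unless first detected or worsening after the dose | no |
| Medical-history tabulation (SAP 5.1) | yes | no, if run on the Safety population as SAP 3.1 says |
| Data listings (SAP 3.1) | yes, as medical history | yes, as medical history |

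Other readable passages that might widen the window:

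- **Protocol 8** refers to events "considered related to the study treatment or other aspects of the study". This shows that procedure-related harm is meant to be in scope, but the clause describes which events are followed up, not when collection begins.
- **Protocol 8.1, last part,** asks for notification of SAEs reasonably related to study participation, but only when the investigator learns of them after discharge from the study.
- **Appendix 4, AE definition,** ties an AE to use of a medicinal product. A dye reaction may satisfy that, but meeting the definition does not change the collection dates.
- **Appendix 4, events meeting the definition,** includes conditions first detected after dosing. A reaction recognised before the injection does not qualify.

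None of these moves the start of collection.

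Size, counted as procedures:

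- Participants: up to 30 (Protocol synopsis; SAP 2.3).
- Angiograms per participant: 3 (Day 0, Day 28, Day 84).
- Planned maximum: 30 × 3 = 90.
- Before collection starts: 30 × 1 = 30.
- Share: 30 / 90 = 33%.

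If k further people have a baseline angiogram and then fail eligibility on Day 0, the share becomes (30 + k) / (90 + k), which is above one third. The documents give no value for k.

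**The case against.** **Serious pre-dose events never reach the sponsor.** A reader might infer this from 8.1. The documents do not support it. Protocol 8.1 refers to Appendix 4 for SAE reporting, and the reporting block there is redacted, so a pre-dose or procedure-related rule could be in it. This objection stands. What remains is that such a rule would contradict the unredacted text of 8.1 and SAP 5.1.

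**The events vanish from the record.** This is also too strong. SAP 5.1 tabulates them as medical history and SAP 3.1 puts all data into listings. They are kept, but under a label that does not identify them as adverse events.

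**The Schedule of Activities contradicts 8.1.** The Predose mark may be only a baseline score on the symptom scale: the row combines two items, its footnote describes that scale, and the Day 0 text mentions symptoms alone. The row is ambiguous and does not prove a contradiction.

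**A reaction before any AVD-104 exposure says nothing about AVD-104.** This is correct, and it is a good reason to keep such events out of the treatment-emergent tables and to leave an undosed person outside the Safety population. It is not a reason to record harm from a required procedure as background history.

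**The rule is deliberate and identical in both documents.** True. The point is that a stated rule gives a poorer safety record than a cheap alternative; it is not that something was left out.

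**Conclusion.** The point holds on the readable text. AE and SAE collection opens at the first injection, required procedures come before it, and no exception covers serious or procedure-related events. Harm from those procedures is therefore recorded and listed as medical history, and a participant who is then not dosed contributes to no Safety-population table.

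At full enrolment this affects up to 30 of 90 planned angiograms, together with the screening procedures. It measures exposure to the gap and not expected events, because no event rate is given. Efficacy results and treatment-emergent tables are unaffected.

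The conclusion rests on two assumptions: that the two sentences of 8.1 are read together as exhaustive, and that the redacted SAE block does not override them. If it does, the passages conflict and must be reconciled, so 8.1 and SAP 5.1 need revision in either case.

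**What to change.** - In Protocol 8.1 and SAP 5.1, collect AEs and SAEs related to protocol-required procedures from signed consent, for all consented participants.
- Send those SAEs through the existing SAE route, and check the Appendix 4 reporting text against the revised window.
- Flag these events as pre-treatment and give them a separate listing that is not restricted to the Safety population.
- Keep the treatment-emergent tables counted from the first injection, and leave unrelated pre-dose occurrences in medical history.
- Align the combined review row in the Schedule of Activities and the Day 0 visit text with the new window. State whether the Predose mark means a symptom score, an adverse event query or both, and provide for events that arise after the angiogram and before the injection.

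The cost is a short change to each document, one data flag, one listing and a few extra pre-dose AE forms.
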